Post-acute Care Preferred Provider Network Skilled Nursing Facility Selection as a Function of Repisodic Mobile Application Settings

Statistical Analysis Plan

February 16, 2023

Statistical Analysis Plan

Brief Summary

This study tests whether changing the relative order of presentation of post acute care skilled nursing facilities (SNFs) in the Repisodic application, i.e., presenting preferred SNFs (P-SNFs) first, increases selection of, and discharges to, P-SNFs and decreases lengths of stay (LoS) for Geisinger patients discharged to SNFs. Along with the order of P-SNFs, the study also assesses whether a short video reviewing the benefits of care coordination in P-SNFs increases patient election to transfer to one.

Randomization

Case managers were randomized to one of two conditions upon their account creation (Default List vs. P-SNF Top-Sorted List). Patients were independently randomized to one of two conditions when Repisodic lists were generated for them (Full List/Full Map/Default Video vs. P-SNF List/P-SNF Map/P-SNF Video).

Project Status

All interventions were launched on 5/28/2021 and data collection is ongoing. Outcome data have not been examined as a function of experimental condition. However, only patients who are ultimately discharged to a SNF can be included in our analyses, and not all randomized patients are ultimately discharged to SNFs (e.g., patients who were discharged home, despite initially being considered for a SNF). So, to assess enrollment progress throughout the study, we need to extract data on patients' discharge locations and remove patients who were not discharged to a SNF.

Our original primary outcome time frame was 12 months or as long as it takes to reach N=4,000, whichever occurs first. However, we decided to extend our outcome time frame to 24 months or as long as it takes to reach N=5,000 patients. We made this change because we noticed an imbalance in the number of case managers assigned to the two conditions, such that by chance, there were more active case managers in the P-SNF top-sorted condition (N = 104 as of 1/2/23) compared with the default list condition (N = 70 as of 1/2/23). We ran a simulation power analysis to reassess how many patients should be in our final sample size, given the imbalance in case manager assignment, and determined that 5,000 patients would yield sufficient power to detect a 4% increase in P-SNF selection.

However, by the time we made the decision to change our inclusion criteria, enrollment exceeded 5,000 patients. We plan to include all eligible patients enrolled through 1/2/23 in analyses, because we have already pulled enrollment data on these patients.

Power Analysis

Data will be collected from 5,000 patients who were discharged to SNFs. We expect to have 80% power to detect a 4% increase (34% to 38%) in selection of P-SNFs at two-tailed p < .05.

Analysis Approach

Analyses described below represent our planned analyses assuming statistical assumptions are met. If assumptions are not met, we will run alternative tests appropriate for the outcome distribution (e.g., non-parametric tests).

Recent work suggests that OLS regressions are appropriate in randomized experiments with binary outcome variables such as ours (Gomilla, 2021). Therefore, for binary outcome variables, we default to running OLS regressions.

Some of our originally preregistered outcome descriptions mentioned comparing Time 1, before the Repisodic app was deployed, to Time 2, during the study, after launch of the app. Upon learning that it is infeasible to obtain comparable Time 1 measurements and include them in analysis, we decided to omit Time 1 to focus analyses entirely on comparing outcomes during the study period (i.e., the primary causal investigation).

Primary Outcomes

P1: Overall LoS (system/case manager level) [Time Frame: 24 months or as long as it takes to reach N=5,000, whichever occurs first]

Difference in LoS (in days) for patients as a function of case manager study condition

Analysis: We will run a gamma regression to test whether LoS differs between patients with a case manager in Default List versus P-SNF Top-Sorted groups.

P2: P-SNF placement (system/case manager level) [Time Frame: 24 months or as long as it takes to reach N=5,000, whichever occurs first]

Difference in proportion of discharges of patients to P-SNFs (out of P-SNFs + NP-SNFs) as a function of case manager study condition.

Analysis: We will run a beta regression to test whether there is a difference in the proportion of patient discharges to P-SNFs for the case manager Default List and P-SNF Top-Sorted groups.

P3: P-SNF pre-selection (case manager level) [Time Frame: 24 months or as long as it takes to reach N=5,000, whichever occurs first]

Number of P-SNFs selected by case managers for inclusion in the patients' lists, to assess the direct impact of Repisodic changes on case manager behavior; this is the first decision in the process, before patients' selections and SNF availability factor into the final discharge decision and placement.

Analysis: We will run a negative binomial regression to test whether the number of P-SNFs preselected differs as a function of case manager study arm, clustering standard errors at the case manager level. P4: P-SNF selection (case manager level) [Time Frame: 24 months or as long as it takes to reach N=5,000, whichever occurs first]

Number of P-SNFs selected by patients to help assess the downstream impact of Repisodic changes on patient behavior following case manager pre-selection, again omitting the influence of SNF availability.

Analysis: We will run a negative binomial regression to test whether the number of P-SNFs selected differs as a function of case manager condition, clustering standard errors at the case manager level.

Note: Retrospective data prior to the study period suggested that only ~15% of patients indicate their selections in the Repisodic app. Therefore, data will be missing for many patients in this analysis. However, we will run this analysis on patients with available data.

P5: P-SNF percent selected (case manager level) [Time Frame: 24 months or as long as it takes to reach N=5,000, whichever occurs first]

Percentage of patients who selected at least one P-SNF, to help assess the downstream impact of Repisodic changes on patient behavior following case manager pre-selection.

Analysis: We will run a beta regression to test whether the percentage of patients who selected one or more P-SNFs differs as a function of case manager condition, clustering standard errors at the case manager level.

Note: Retrospective data prior to the study period suggested that only ~15% of patients indicate their selections in the Repisodic app. Therefore, data will be missing for many patients in this analysis. However, we will run this analysis on patients with available data.

P6: LoS (patient/caretaker level) [Time Frame: 24 months or as long as it takes to reach N=4,000, whichever occurs first]

LoS for patients (in days).

Analysis: We will run a gamma regression to test whether LoS differs as a function of patient condition, clustering standard errors at the case manager level.

P7: P-SNF placement (patient/caretaker level) [Time Frame: 24 months or as long as it takes to reach N=5,000, whichever occurs first]

Patient was discharged to a P-SNF: yes/no.

Analysis: We will run an OLS regression to test whether patient P-SNF placement rates differ as a function of patient condition, clustering standard errors at the case manager level.

P8: P-SNF selection (patient/caretaker level) [Time Frame: 24 months or as long as it takes to reach N=5,000, whichever occurs first]

Patient selected a P-SNF for discharge: yes/no. This is a more direct reflection of patient behavior, not yet moderated by bed availability and other real-world considerations that affect Outcome 7.

Analysis: We will run an OLS regression to test whether patient P-SNF selection rates differ as a function of patient condition, clustering standard errors at the case manager level.

Note: Retrospective data prior to the study period suggested that only ~15% of patients indicate their selections in the Repisodic app. Therefore, data will be missing for many patients in this analysis. However, we will run this analysis on patients with available data.

Secondary Outcomes

S1: Time to pre-select a SNF (case manager level) [Time Frame: 24 months or as long as it takes to reach N=5,000, whichever occurs first]

Time to pre-select a SNF/SNF list in Repisodic (in minutes), from the time that the case manager first signs into the iPad to when the case manager saves the list to send to the patient. This measure excludes cases in which the task was not completed.

Analysis: We will run an OLS regression to test whether the time to pre-select a SNF list in Repisodic differs as a function of case manager condition, clustering standard errors at the case manager level.

S2: Time to select a SNF (patient/caretaker level) [Time Frame: 24 months or as long as it takes to reach N=5,000, whichever occurs first]

Time to select a SNF in Repisodic (in minutes), from the time that the patient first signs or is signed into the iPad to when the patient clicks to send the list to the case manager. This measure excludes cases in which the task was not completed.

Analysis: We will run an OLS regression to test whether the time to select a SNF list in Repisodic differs as a function of patient condition, clustering standard errors at the case manager level.

Note: Retrospective data prior to the study period suggested that only ~15% of patients indicate their selections in the Repisodic app. Therefore, data will be missing for many patients in this analysis. However, we will run this analysis on patients with available data.

Other Outcome Measures

O1: LoS for patients who had a P-SNF as an option (patient/caretaker level) [Time Frame: 24 months or as long as it takes to reach N=5,000, whichever occurs first]

LoS for patients (in days). Excluding patients who did not have at least one P-SNF on the full list they were provided.

Analysis: We will run a gamma regression to test whether LoS differs as a function of patient condition, clustering standard errors at the case manager level.

O2: P-SNF placement for patients who had a P-SNF as an option (patient/caretaker level) [ Time Frame: 24 months or as long as it takes to reach N=5,000, whichever occurs first]

Patient was discharged to a P-SNF: yes/no. Excluding patients who did not have at least one P-SNF on the full list they were provided.

Analysis: We will run an an OLS regression to test whether patient P-SNF placement rates differ as a function of patient condition, clustering standard errors at the case manager level.

O3: P-SNF selection for patients who had a P-SNF as an option (patient/caretaker level) [Time Frame: 24 months or as long as it takes to reach N=5,000, whichever occurs first]

Patient selected a P-SNF for discharge: yes/no. Excluding patients who did not have at least one P-SNF on the full list they were provided. This is a more direct reflection of patient behavior, not yet moderated by bed availability and other real-world considerations that affect Outcome O2.

Analysis: We will run an an OLS regression to test whether patient P-SNF selection rates differ as a function of patient condition, clustering standard errors at the case manager level.

Note: Retrospective data prior to the study period suggested that only ~15% of patients indicate their selections in the Repisodic app. Therefore, data will be missing for many patients in this analysis. However, we will run this analysis on patients with available data.

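### The SAP states the video's effect on P-SNF election as an aim, but list, map and video change together between the patient arms, so only the package effect can be estimated

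*SAP*

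**What the plan says.** The Brief Summary gives the study two questions. The first is about the order in which SNFs are presented. The second is about the video: "the study also assesses whether a short video reviewing the benefits of care coordination in P-SNFs increases patient election to transfer to one".

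The Randomization section describes two independent allocations:

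- Case managers: "Case managers were randomized to one of two conditions upon their account creation (Default List vs. P-SNF Top-Sorted List". Only list order differs.
- Patients: "Patients were independently randomized to one of two conditions when Repisodic lists were generated for them". The conditions are "Full List/Full Map/Default Video vs. P-SNF List/P-SNF Map/P-SNF Video", so list, map and video all differ between them.

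Four outcomes measure whether a patient chose or went to a P-SNF at the patient level. P7 (primary) and O2 test whether "patient P-SNF placement rates differ as a function of patient condition"; P8 (primary) and O3 test whether "patient P-SNF selection rates differ as a function of patient condition". No analysis in the SAP has a term for the video.

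**The concern.** The aim is a causal claim about one component, while the randomised contrast is about three components that move together. The video is completely confounded with the list and the map, and the Brief Summary never mentions the map.

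Someone reading the results against the stated aims would match the case manager arm to list order and the patient arm to the video. A positive P7, P8, O2 or O3 would then be read as evidence that the video works, although the list or the map could have produced all of it. A null result would be read as evidence that the video does nothing, which the data do not support either. The risk lies in the conclusion drawn, not in the estimate or its p-value.

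**Working it through.** **The plan's own figure.** The only numerical claim nearby is "80% power to detect a 4% increase (34% to 38%) in selection of P-SNFs" with 5,000 patients at two-sided 0.05. With the usual two-proportion formula, power = Φ[(0.04 − 1.96·SE₀)/SE₁], where SE₀ uses the pooled rate and SE₁ the two separate rates:

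- 2,500 per arm: SE₀ = √(2 × 0.36 × 0.64/2,500) = 0.01358 and SE₁ = √((0.34 × 0.66 + 0.38 × 0.62)/2,500) = 0.01356, so power is 83.8%.
- Patients split 70:104, like the case managers (about 2,011 and 2,989): 82.3%.
- The same split with an assumed ICC of 0.002 and equal clusters of 5,000/174 = 28.7 patients: design effect 1 + 27.7 × 0.002 = 1.055, power 80.3%. The SAP gives no ICC.

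The stated 80% is therefore broadly reproduced. It is not an input to this point, which concerns what can be estimated and not how precisely.

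**Inputs.** The two randomisations, each with two levels, come from the Randomization section. Crossing them gives 4 cells. Let C be case manager order (0 or 1) and T the patient condition (0 or 1). Because the components switch together, list = map = video = T.

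**Design matrix.**

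| C | T | intercept | C | list | map | video |
|---|---|---|---|---|---|---|
| 0 | 0 | 1 | 0 | 0 | 0 | 0 |
| 0 | 1 | 1 | 0 | 1 | 1 | 1 |
| 1 | 0 | 1 | 1 | 0 | 0 | 0 |
| 1 | 1 | 1 | 1 | 1 | 1 | 1 |

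The last three columns are identical, so the rank is 3 for 5 parameters.

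**Estimability.** A contrast is estimable only if it is a linear combination of the rows. Every row has equal entries for list, map and video, so every estimable contrast does too.

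- Case manager order (0, 1, 0, 0, 0) is estimable.
- The package (0, 0, 1, 1, 1) is estimable.
- Video alone (0, 0, 0, 0, 1) is not, and neither is list alone or map alone.

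Adding the case manager by patient condition interaction gives rank 4 for 6 parameters, and the video remains inestimable. More patients repeat the same rows and leave the rank unchanged.

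**Illustration.** Assume that 34% to 38% is the patient-condition difference, that case manager order has no effect, and that no component lowers P-SNF choice. The cells are in the order of the table above.

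| Video share (points) | List + map share (points) | Cell means (%) |
|---|---|---|
| 0 | 4 | 34, 38, 34, 38 |
| 1 | 3 | 34, 38, 34, 38 |
| 2 | 2 | 34, 38, 34, 38 |
| 3 | 1 | 34, 38, 34, 38 |
| 4 | 0 | 34, 38, 34, 38 |

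The data would be the same in every row. If a component could lower P-SNF choice, the video's share would not be bounded at all.

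**The case against.** The strongest reply is that the operative text is sound. The sentence at issue is a one-line overview, the section after it discloses both patient conditions in full, and no outcome or model is labelled a video effect. The sentence can also be read loosely, as naming the most conspicuous new element of the patient arm. A missing caution about interpretation is a reporting matter. This lowers the weight of the point but does not remove it: the sentence makes the video the subject of a causal question, and disclosing the bundle a paragraph later leaves that question unanswerable.

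A second reply concerns scope. Election corresponds most directly to selection (P8, O3). Placement (P7, O2) also depends on bed availability, and O2 and O3 repeat P7 and P8 in a subset. The core is indeed P8 and O3. But the aim speaks of electing to transfer, and placement bears on that too, so all four stay in.

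A third reply is that the 0 to 4 point range borrows a figure that Project Status links to the imbalance in case managers, and so only says that a share of an assumed total lies between none and all of it. That is fair. The range is illustrative, and the rank result does not depend on it.

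Finally, the bundling was a design choice and cannot be undone now that the interventions have run. That is why only wording is at issue.

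**Conclusion.** The point holds. The SAP states an aim that its own two patient conditions cannot answer. The effect of the list, map and video together is estimable and validly randomised; the effect of the video alone is not, at any sample size. This rests only on the Randomization section's description of the arms, and no account in another document could make the video separable under those arms.

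Four outcomes are affected, two of them primary: P7, P8, O2 and O3. P6, O1 and S2 use the same patient contrast but measure length of stay or time, so they do not bear on this aim. No estimate, standard error or p-value changes. The consequence is limited to what may be concluded, and the correction should be made before the results are read.

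**What to change.** Replace the video sentence in the Brief Summary with wording such as: *The study also assesses the effect of the combined patient-facing P-SNF package (list, map and video), compared with the full/default package, on P-SNF selection (P8, O3) and placement (P7, O2).* Then add: *No effect will be attributed to the video, the list or the map alone.*

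Make the change now, while Project Status can still say "Outcome data have not been examined as a function of experimental condition", so that it cannot appear to follow from the results.

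The cost is two sentences and a narrower claim: the study gives up a stated conclusion about the video. Data, models and sample size stay as they are.

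### Outcomes recorded in the app before discharge, above all P3 and S1, are limited to patients later discharged to a SNF, a filter they do not need and that acts after both randomisations

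*SAP*

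**What the plan says.** The population rule is under Project Status: "only patients who are ultimately discharged to a SNF can be included in our analyses". The same paragraph acknowledges that some randomised patients go elsewhere, for instance home, and says that enrolment is tracked by a step to "extract data on patients' discharge locations and remove patients who were not discharged to a SNF". The Power Analysis section likewise counts 5,000 SNF-discharged patients.

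Both randomisations come earlier. Under Randomization: "Case managers were randomized to one of two conditions upon their account creation", and "Patients were independently randomized to one of two conditions when Repisodic lists were generated for them".

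Several outcomes are described as preceding placement:

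- **P3**, the number of P-SNFs the case manager pre-selects: "this is the first decision in the process, before patients' selections and SNF availability factor into the final discharge decision and placement".
- **P4**, the number of P-SNFs the patient selects: "again omitting the influence of SNF availability". P5 is the percentage selecting at least one.
- **P8** and **O3**, P-SNF selection yes/no, are described as not yet affected by bed availability.
- **S1** stops when the case manager saves the list. **S2** stops when the patient sends the list back.

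None of these entries lifts the SNF-only rule. For P4, P5, P8, S2 and O3 the SAP adds that only about 15% of patients were found to record selections in the app.

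**The concern.** Randomisation makes the arms comparable at the time it happens. A filter applied later keeps them comparable only if the intervention does not affect who passes it. SNF discharge comes after the case manager has seen the sorted or default list, and after the patient has been assigned a list, map and video. If any of these changes the proportion or type of patients who accept SNF care, the retained groups are no longer the randomised ones.

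For some outcomes the filter follows from the definition. P2 has SNF discharges as its denominator, and the Brief Summary frames length of stay as that of patients discharged to SNFs. P3 and S1 are different. They are complete once the list is saved, and their value exists whether the patient later goes to a SNF or home. The SAP presents P3 as the direct effect on case manager behaviour, free of later influences, and then selects its patients on a later event. It gives no reason for this, and it plans neither a comparison of SNF-discharge rates by arm nor an analysis in all randomised patients.

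**Working it through.** **1. The plan's own figure.** The only related figure is 80% power for 34% versus 38% with 5,000 patients, two-sided 0.05. With 2,500 per arm and no clustering:

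- Null standard error = √(2 × 0.36 × 0.64 / 2,500) = 0.01358.
- Alternative standard error = √((0.34 × 0.66 + 0.38 × 0.62) / 2,500) = 0.01356.
- Power = Φ((0.04 − 1.96 × 0.01358) / 0.01356) = 83.8%.

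At the 70:104 case manager split (about 2,011 versus 2,989 patients) it is 82.3%. A design effect of about 1.06 (70:104) to 1.11 (1:1) brings either to 80%. With 5,000/174 ≈ 29 patients per case manager, that is an intracluster correlation of about 0.002 to 0.004. The SAP's figure comes from a simulation whose clustering inputs are not given, so it cannot be reproduced exactly, but it is plausible. The present point does not depend on it.

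**2. Order of events.** Case manager randomisation (account creation) → patient randomisation (list generation) → pre-selection (P3, S1) → patient selection (P4, P5, P8, S2, O3) → discharge destination (the filter). Seven outcomes lie before the filter. P1, P2, P6, P7, O1 and O2 concern placement or length of stay.

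**3. How many patients are dropped.** The SAP does not say. If 50% to 90% of randomised patients reach a SNF (assumption), 5,000 SNF discharges correspond to 5,000/0.5 = 10,000 down to 5,000/0.9 ≈ 5,556 randomised patients. The filter would then remove about 5,000 down to 556.

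**4. How far the filter could move a result.** Let a share s of one arm and s + d of the other reach a SNF. Assume no true effect on selection, a selection rate of 34% among the share s, and a rate q among the added patients. Then:

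shift = (0.34s + dq)/(s + d) − 0.34 = d(q − 0.34)/(s + d)

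| s versus s + d (assumed) | q = 0% | q = 100% |
|---|---|---|
| 70% versus 72% | (0.238 + 0)/0.72 − 0.34 = −0.9 points | (0.238 + 0.02)/0.72 − 0.34 = +1.8 points |
| 70% versus 75% | (0.238 + 0)/0.75 − 0.34 = −2.3 points | (0.238 + 0.05)/0.75 − 0.34 = +4.4 points |

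If d = 0 and the same kind of patient passes the filter in both arms, the shift is zero. The two columns are the extremes of q, so realistic values lie between them.

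The SAP gives no mean for P3 or S1, so no shift in their own units can be stated. By the same formula the shift in a mean is d/(s + d) times the difference between the added patients and the rest: 0.02/0.72 = 2.8% of that difference, or 0.05/0.75 = 6.7%.

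**5. Who gains from lifting the filter.** P3 and S1 carry no 15% note, so nearly all dropped patients could return (S1 still leaves out uncompleted tasks). For P4, P5, P8, S2 and O3, about 85% of patients would remain missing for a different post-randomisation reason.

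**The case against.** **The removal step only tracks enrolment.** That is true of the sentence about extracting discharge locations. The sentence before it, however, governs the analyses themselves.

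**SNF-discharged patients are the target population, and the restriction is disclosed.** This is a fair defence for the outcomes tied to SNF discharge, and their SNF-only set should stay. It has some force for P8, because a selection for discharge means less for someone who went home. It does not explain why P3 or S1 needs the filter.

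**The interventions may not move anyone between home and SNF.** This stands as a limit. The case manager arm changes only the order of SNFs, and nothing in the SAP says that this alters SNF acceptance. The patient arm also changes list, map and video, so an effect is conceivable, but there is no evidence of one.

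**The 15% recording rate matters more.** This is conceded for P4, P5, P8, S2 and O3. It is no reason to add a second filter, but it does make the gain there small.

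**A stronger reading.** A reader might infer that the filter creates a false rise in P-SNF placement (P2, P7) close to the 4-point target. For example, if 2 more points of one arm's patients enter SNF care, all to P-SNFs, the P-SNF share rises by (0.4 × 0.34 + 0.02)/0.42 − 0.34 = 3.1 points at an assumed SNF share of 40%, and by 1.6 points at 80%. The document does not support that reading, for three reasons:

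- P-SNF discharge among all randomised patients would truly rise by 2 points in that scenario. The estimand differs, and the effect is not false.
- The 34% is the SAP's baseline for selection, not for discharge share.
- Sending every added patient to a P-SNF is the extreme case.

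**Conclusion.** The point holds in a limited form. The SAP conditions every outcome on an event after both randomisations. For P3 and S1, which are complete before discharge, this is unnecessary: it drops randomised patients and leaves the comparison open to bias. The same applies in principle to P4, P5, P8, S2 and O3, with little to gain while about 85% of selections are unrecorded.

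The size is unknown, because the SAP gives no SNF-discharge share, overall or by arm. The −0.9 to +1.8 points is an illustration that rests on an assumed 70% versus 72% reaching a SNF, no true effect, and an added-patient selection rate anywhere from 0% to 100%. It does not show that the results are biased, and it is not a reason to abandon the SNF-only placement and length-of-stay analyses. This is an inexpensive improvement. It can still be prespecified, since the SAP states that outcomes have not been examined by condition.

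**What to change.** 1. **P3 and S1:** make the primary analysis include all patients for whom a list was generated, whatever the discharge destination. S1 keeps its exclusion of uncompleted tasks.
2. **P4, P5, P8, S2 and O3:** use all such patients with a recorded selection, O3 keeping its condition of a P-SNF on the full list. State that the roughly 15% recording rate is a separate post-randomisation restriction that this step does not remove.
3. **P1, P2, P6, P7, O1 and O2:** keep the SNF-only set.
4. **Check on the filter:** compare the proportion discharged to any SNF between arms, separately for the case manager factor and the patient factor.
5. **Sensitivity analysis:** analyse P-SNF discharge (yes/no) among all randomised patients, reported as a different estimand and not as a correction of P2 or P7.

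The cost is a few extra models. Discharge locations have to be extracted anyway to apply the present rule. App data must be retained for patients not discharged to a SNF, and the SAP does not say whether they are. The all-patient placement effect will be diluted by home discharges and should be read with that in mind.

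### The SAP's fallback lets any planned test be replaced, after the data are seen, by an unnamed one that need not respect randomisation by case manager

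*SAP*

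**What the plan says.** The Analysis Approach section of the SAP opens with a condition: "Analyses described below represent our planned analyses assuming statistical assumptions are met". It continues: "If assumptions are not met, we will run alternative tests appropriate for the outcome distribution (e.g., non-parametric tests". Both sentences precede all the outcome sections, so they cover P1-P8, S1-S2 and O1-O3. The only criterion for choosing the alternative is the outcome's distribution.

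The same section defends linear regression for yes/no outcomes on the strength of a cited methods paper, and concludes that "for binary outcome variables, we default to running OLS regressions".

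The Randomization section describes two factors with different units. For list order: "Case managers were randomized to one of two conditions upon their account creation (Default List vs. P-SNF Top-Sorted List". For list, map and video: "Patients were independently randomized to one of two conditions when Repisodic lists were generated for them". Project Status reports "more active case managers in the P-SNF top-sorted condition (N = 104 as of 1/2/23", "compared with the default list condition (N = 70 as of 1/2/23".

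The planned models for P3, P4, P5 and S1 (manager-randomised) and for P6-P8, S2 and O1-O3 (patient-randomised) all have standard errors clustered by case manager. P1 (gamma) and P2 (beta) state no clustering.

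**The concern.** Three things are left open.

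- **Clustering.** Managers were randomised for P1-P5 and S1, so patients of one manager are not independent replicates of the list-order condition. An alternative chosen only to suit the outcome's distribution may treat them as if they were. The usual two-sample rank test, applied to patients, does so. For P3, P4, P5 and S1 that would drop a safeguard the planned model has. S1 shows how this could arise: "We will run an OLS regression to test whether the time to pre-select a SNF list in Repisodic differs", with the outcome a time in minutes that may well be skewed.
- **Choice after the data.** No diagnostic, threshold or blinding of the check is stated, so the primary test is not settled until the data have been looked at.
- **Target.** P1 is defined as a difference in days. A rank test answers a different question, and its p-value cannot simply be attached to a difference in mean days.

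At stake is a primary result declared significant by a test whose true error rate is well above 5%, or one that speaks to something other than the stated effect.

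**Working it through.** **Inputs.** From the SAP: 104 and 70 managers, so 174 in all; 5,000 patients (Power Analysis); about 15% of patients recording a selection (notes to P4 and P5). Derived: 5000/174 = 28.7 patients per manager, and 0.15 × 5000 = 750, 750/174 = 4.3 responders per manager. Assumed: ICC from 0.01 to 0.10, because the SAP gives none.

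**The SAP's own figure.** The stated 80% power for 34% against 38% at two-sided 0.05 is the only figure that can be recomputed. Without clustering, 5,000 patients give 83.8% at 1:1 and 82.3% at 70:104. Power is exactly 80% at an ICC of 0.0038 (1:1) or 0.0022 (70:104). The SAP used a simulation whose inputs it does not state, so the gap shows no error, and the point here does not depend on it.

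**Type I error of a test that ignores managers.** Design effect DE = 1 + (m − 1) × ICC. True rejection rate of a nominal 5% test = 2 × [1 − Φ(1.96/√DE)]. For example, at m = 28.7 and ICC 0.05, DE = 1 + 27.7 × 0.05 = 2.387 and the rate is 20.5%. The simulation column is a patient-level Mann-Whitney test under a true null (174 managers split 104:70, 29 patients each, skewed stay, 2,000 runs).

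| ICC | DE, m = 28.7 | Formula | Simulation | DE, m = 4.3 | Formula |
|---|---|---|---|---|---|
| 0.01 | 1.277 | 8.3% | 8.4% | 1.033 | 5.4% |
| 0.02 | 1.555 | 11.6% | 11.7% | 1.066 | 5.8% |
| 0.05 | 2.387 | 20.5% | 20.3% | 1.166 | 6.9% |
| 0.10 | 3.774 | 31.3% | 31.3% | 1.331 | 8.9% |

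A repeat of the simulation gave 8%, 10%, 20% and 32%. The m = 28.7 columns bear on P1, P3 and S1 (S1 less so if many incomplete tasks are excluded); the m = 4.3 columns bear on P4 and P5.

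**Two comparisons.** A rank test on manager means (n = 174) rejected 3.9-5.3% over ICCs from 0 to 0.10. For the patient-randomised factor, the patient-level rank test rejected 4.4-5.8% over the same range. The inflation therefore comes from ignoring the unit of randomisation, not from ranks as such.

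**Target, length of stay.** Take two gamma distributions with the same mean of 6 (shape 2, scale 3; shape 1.5, scale 4) and 2,500 per arm. Mann-Whitney rejected in 76% of 400 runs and a test of means in 4.5%. A rank result can be strongly positive when mean days do not differ.

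**Target, yes/no outcomes.** With 950/2500 against 850/2500 (38% against 34%), the p-values are 0.00322 (Mann-Whitney), 0.00322 (chi-square) and 0.00321 (linear regression). The rank effect is 0.52 = 0.5 + 0.04/2, so the contrast is the same.

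**Beta regression at the boundary.** Beta regression cannot take 0% or 100%. Assuming four responders per manager and 36% selecting (the midpoint of 34% and 38%), the share of managers at a boundary for P5 is 0.64⁴ + 0.36⁴ = 0.168 + 0.017 = 0.185, or about 18%.

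**The case against.** The strongest reply is that the SAP does not order a rank test. Non-parametric tests are only an example, and a permutation test at the unit of randomisation or a rank test on manager summaries would qualify and be valid. That is right: the defect is that the SAP permits an invalid replacement, not that it prescribes one.

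A reader might also infer more than the document supports:

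- *That the fallback must fire for P7, P8, O2 and O3*, because linear regression on a yes/no outcome violates its textbook assumptions. The SAP defends that choice explicitly, so the rule need not fire there. Nor does the SAP call for a formal goodness-of-fit test for the other outcomes.
- *That the target changes for every outcome.* It does not for yes/no outcomes, as shown above.
- *That planned clustering is lost for all manager-randomised outcomes.* P1 and P2 state none to begin with. Among these outcomes only P3, P4, P5 and S1 could lose it, and if P2 or P5 is analysed as one proportion per manager, a rank test on those proportions respects the clusters.
- *That the open choice has a known cost in type I error.* Reporting the smaller of a mean-test and a rank-test p-value rejects 7.2% under the null (500 per arm), but picking by p-value is not the SAP's rule. Project Status says outcomes had not been examined by condition, although it does not say that later assumption checks will be blinded.

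Finally, if the SAP's 80% power already allows for clustering, the back-calculated ICC of about 0.002-0.004 would mean inflation to only about 5.6-6.3%. That inference concerns P-SNF selection and rests on unstated simulation inputs. It does not bound the ICC for pre-selection counts or times, which are the manager's own behaviour.

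**Conclusion.** The concern stands in limited form. The SAP lets any planned analysis be exchanged, after the data are seen, for an unnamed test chosen only for the outcome's distribution, with no duty to respect randomisation by case manager.

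If that test were a patient-level rank test, the error rate would be about 8% to 31% for P3 and S1, where planned clustering would be lost, and for P1, which states none. It would be about 5-9% for P4 and P5, and about 5% for patient-randomised outcomes. These figures rest on assumed ICCs of 0.01 to 0.10 and on every patient contributing to P1, P3 and S1. The change of target is real for length of stay and times, and broadly for counts.

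Some fallback is still needed. Locking in every named model whatever the data show would be a mistake for P2 and P5, because beta regression cannot handle managers at 0% or 100%.

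**What to change.** Before outcomes are examined by condition, replace the switching sentence with a fixed rule:

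1. For length of stay, counts, times and yes/no outcomes, the named mean model with standard errors clustered by case manager is primary, whatever distributional checks show. This adds the clustering that P1 lacks.
2. For P2 and P5 where managers have 0% or 100%, and for any model that cannot be fitted, use one alternative: a difference in means or proportions tested by permutation at the unit of randomisation. Permute manager labels for P1-P5 and S1, and patient labels for P6-P8, S2 and O1-O3.
3. Any rank test is reported as a sensitivity analysis only.

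The cost is SAP wording and a few lines of code for the permutation test. No additional data are needed.
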